3.2 Study Outcome Measures

3.2.1 Primary Outcome Measures

The primary endpoint/outcome measure is the DOOR at Outcome Assessment Visit #1.

DOOR is defined as follows:

- I. Each subject is evaluated according to the ordinal composite outcome (See Table 1 below) and assigned an outcome rank ranging from 1-8.
- II. Desirability of Outcome Ranking (DOOR) is then assigned according to two rules:
 - (i) When comparing two subjects with different ordinal responses, the subject with a better ordinal response receives a higher rank.
 - (ii) When comparing two subjects with identical ordinal responses, the subject with fewer days of antibiotic use receives a higher rank.

The ordinal composite outcome involves an assessment of whether the subject has an adequate clinical response and whether they have experienced any solicited events as defined below.

Table 1. Ordinal Outcome

	Adequate clinical response¹ (Assessed at Outcome Assessment Visits #1 and #2)	Solicited events³ (Assessed at Outcome Assessment Visits #1 and #2)
1	Yes, with resolution of symptoms ²	None
2	Yes, with resolution of symptoms ²	Mild (Grade 1)
3	Yes, with resolution of symptoms ²	Moderate (Grade 2)
4	Yes, with resolution of symptoms ²	Severe (Grade 3)
5	Yes, with persistent symptoms of fever, tachypnea, or cough	None or any grade
6	No, with ED/clinic visit but no hospitalization	None or any grade
7	No, with hospitalization	None or any grade
8	Death from any cause	

¹Adequate clinical response is defined as the absence of a medically attended visit to an ED or outpatient clinic or hospitalization for persistent or worsening pneumonia that occurs after randomization and receipt of at least one dose of study drug.

- Persistent or worsening pneumonia is defined as receipt of a non-study systemic antibiotic for pneumonia or treatment for a complication of pneumonia, including drainage of pleural fluid, placement of a chest tube, video assisted thoracoscopic surgery, or thoracotomy procedures.
- Note: Receipt of a non-study antibiotic will not be regarded as satisfying this definition if it is related to a new diagnosis that is unrelated to the prior diagnosis of pneumonia.

²Resolution of symptoms is defined as the absence of all of the following:

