9.5.2 Individual Halting Rules (Termination of Study Product Administration)

Study product administration may be discontinued if any of the following criteria are met:

- Any clinical adverse event (AE), intercurrent illness, or other medical condition occurs that, in the opinion of the investigator, continued receipt of study product would not be in the best interest of the subject;
- New onset of illness or condition that meets exclusion criteria
- Inadequate clinical response that requires off-study antimicrobial therapy.
 - Subjects who require off-study antimicrobial therapy will be defined as having an inadequate clinical response.

Subjects may stop study drug treatment at any time of their own volition or at the advice of their treating provider or the study investigators. Subjects who stop study product for any reason will be regarded as having withdrawn from treatment but not as having withdrawn from the study (i.e, subjects will be asked to continue to participate in follow-up visits). All subjects with an inadequate clinical response will be referred to a non-study healthcare provider for evaluation and possible treatment outside of the clinical study.

At the time of withdrawal, subjects will undergo an early termination visit if they are not willing to participate in the remaining follow-up visits

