6.5.1. Adequate Clinical Response to OAV#1 or OAV#2

Subjects that have no record of receipt of at least one dose of study product will have adequate clinical response and its components considered missing at both OAV#1 and OAV#2. Otherwise, if a subject dies at any point during subject participation in the study, the subject will be considered as not having adequate clinical response at OAV#1 or OAV#2. Otherwise, if a subject does not have OAV#1 then ACR and its components are missing for OAV#1 and if a subject does not have OAV#2 then ACR and its components are missing for OAV#2.

Several variables are used to define the Adequate Clinical Response:

- MAVABRX: Was the subject prescribed or did the subject receive an additional antibiotic treatment at this visit? (Yes/No)
 - o MAVABCP: If Yes, was the antibiotic given for pneumonia or treatment for a complication of pneumonia? (Yes/No)
- MAVPLEUR: Drainage of pleural fluid as treatment for pneumonia or a complication of pneumonia? (Yes/No)
- MAVCHTB: Placement of a chest tube as treatment for pneumonia or a complication of pneumonia? (Yes/No)
- MAVVIDEO: Video assisted thoracoscopic surgery as treatment for pneumonia or a complication of pneumonia? (Yes/No)
- MAVTHOR: Thoracotomy procedure as treatment for pneumonia or a complication of pneumonia? (Yes/No)
- MAVSURG: Any other surgical procedure as treatment for pneumonia or a complication of pneumonia? (Yes/No)
- MAVHOSP: Was the subject hospitalized at this visit? (Yes/No)
 - o MAVHPPN: If Yes, was the hospitalization for the treatment of pneumonia or pneumonia complications? (Yes/No)

If a subject has OAV#1 and did not have a medically attended visit (MAV) from Day 1 to Day 5, inclusive, then the subject had adequate clinical response for OAV#1. If the subject had a MAV from Day 1 to Day 5 for which MAVABRX and MAVABCP were both YES (receipt of a non-

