If a subject has OAV#2 and did not have a medically attended visit (MAV) from Day 1 to Day 18, inclusive, then the subject had adequate clinical response for OAV#2. If the subject had a MAV from Day 1 to Day 18 for which MAVABRX and MAVABCP were both YES (receipt of a non-study systemic antibiotic for pneumonia), or for which MAVPLEUR, MAVCHTB, MAVVIDEO, MAVTHOR, or MAVSURG were YES (treatment for a complication of pneumonia, including drainage of pleural fluid, placement of a chest tube, video assisted thoracoscopic surgery, or thoracotomy procedures), then the subject did not have adequate clinical response at OAV#2. If the subject had a MAV from Day 1 to Day 18 for which MAVHOSP and MAVHPPN were both YES (subject was hospitalized for the treatment of pneumonia or pneumonia complications), then the subject did not have adequate clinical response at OAV#2. Otherwise, if the subject had a MAV from Day 1 to Day 18 and either MAVABRX was missing, MAVABRX was YES and MAVABCP was missing, or any of MAVPLEUR, MAVCHTB, MAVVIDEO, MAVTHOR, or MAVSURG were missing, then adequate clinical response at OAV#2 is missing. Otherwise, if a subject has one or more MAVs from Day 1 to Day 18, with no MAV indicating receipt of a non-study systemic antibiotic for pneumonia or treatment for a complication of pneumonia, including drainage of pleural fluid, placement of a chest tube, video assisted thoracoscopic surgery, or thoracotomy procedures and no hospitalization for treatment of pneumonia or pneumonia complications and no MAV missing data as described, then the subject has adequate clinical response at OAV#2. Note that for determining whether the medical treatment or hospitalization falls within the period of Day 1 to Day 18, the date of the initial MAV will be used (MAVVISDT), rather than specific dates of surgery or hospitalization entered on the MAV form.

The below pseudocode summarizes the logic for defining ACR at OAV#1.

```
if no recorded receipt of study product then ACR_OAV1=missing  
else if death then ACR_OAV1=NO
```

```

else if subject does not have OAV#1 then ACR_OAV1=missing
else if subject has no MAV from Day 1 to Day 5 then ACR_OAV1=YES
else if subject has one or more MAVs from Day 1 to Day 5 with
    (MAVABRX=YES and MAVABCP=YES) or
    MAVPLEUR=YES or
    MAVCHTB=YES or
    MAVVIDEO=YES or
    MAVTHOR=YES or
    MAVSURG=YES or
    (MAVHOSP=YES and MAVHPPN=YES)
    then ACR_OAV1=NO
else if subject has MAV from Day 1 to Day 5 with
    MAVABRX=missing or

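### SAP 6.5.1 scores a child as an adequate response when no medical visit is recorded, even if the concomitant medication form shows a non-study antibiotic for pneumonia

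*SAP*

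**What the plan says.** **Endpoint definition.** Protocol 3.2.1 (Table 1, footnote 1), repeated in SAP 3.3, defines adequate clinical response by the absence of an ED or clinic visit, or a hospitalization, for persistent or worsening pneumonia. A sub-bullet then says what makes a visit count: "Persistent or worsening pneumonia is defined as receipt of a non-study systemic antibiotic for pneumonia", or treatment of a complication. A note exempts unrelated illness: "Receipt of a non-study antibiotic will not be regarded as satisfying this definition if it is related to a new diagnosis" unconnected with the earlier pneumonia. Row 6 of Table 1 is worded as an ED or clinic visit without hospitalization.

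**Derivation.** SAP 6.5.1 reads: "If a subject has OAV#1 and did not have a medically attended visit (MAV) from Day 1 to Day 5, inclusive", then the response at Outcome Assessment Visit (OAV) #1 is adequate. The pseudocode line is "else if subject has no MAV from Day 1 to Day 5 then ACR_OAV1=YES". The rule for the second visit is the same over a longer window: a child who "did not have a medically attended visit (MAV) from Day 1 to Day 18, inclusive, then the subject had adequate clinical response for OAV#2". The antibiotic item behind the derivation, MAVABRX, belongs to a particular visit: "Was the subject prescribed or did the subject receive an additional antibiotic treatment at this visit".

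**Individual halting rules.** Protocol 9.5.2 attaches no visit condition: "Subjects who require off-study antimicrobial therapy will be defined as having an inadequate clinical response".

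**Antibiotic days.** SAP 6.5.6 counts days of antibiotic use from the product administration and concomitant medication records.

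**The concern.** Receipt of a non-study antibiotic for the index pneumonia is the clearest sign in this trial that the assigned course was not enough. SAP 6.5.1 sees that antibiotic only if it was entered on a medical-visit record. If it reached the database only as a concomitant medication, the child can be placed in OCR 1 to 5 instead of 6.

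The SAP then treats one record in two ways. The antibiotic adds days to the DOOR tie-breaker but leaves untouched the ordinal response, which outranks the tie-breaker. The error favors whichever arm has more rescue of this kind. Protocol 2.3.1 names a lower rate of adequate response on short course as the main risk, so the arm most likely to gain is the one whose superiority is being tested. The OCR non-inferiority comparison against 0.40 in SAP 8.2.6 uses the same derivation.

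**Working it through.** **Trace of the SAP 6.5.1 logic.** Take a child who received study product, is alive, has OAV#1, and has a non-study systemic antibiotic for pneumonia started on Days 1 to 5.

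- Antibiotic on the concomitant medication form only, no medical visit in the window: the derivation reaches the no-visit line and returns adequate response before any antibiotic variable is read. OCR is then 1 to 5, according to symptoms and solicited events.
- Same antibiotic entered at a medical visit in the window (MAVABRX and MAVABCP both yes): response is inadequate and, by SAP 6.5.5, OCR is 6 without hospitalization.
- Without OAV#1, response is missing, so the problem does not arise.

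**How other places treat the child in the first case.**

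- Protocol Table 1 and SAP 3.3: adequate, because no visit occurred. SAP 6.5.1 agrees.
- Protocol 9.5.2: inadequate.
- Protocol 2.3.1, repeated in SAP 4.2: adequate response includes not needing further antibiotics, so inadequate.
- SAP 8.3.3: says that children given off-study antibiotic not unrelated to the pneumonia will have a higher (worse) OCR. Section 6.5.1 does not ensure this.
- SAP 6.5.6: the antibiotic days are counted.

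**Design effect, for scale.** SAP section 5 sets the DOOR probability at 0.60 against 0.50 under the null. Its formula gives N = (1.960 + 1.282)² / [12 × 0.5 × 0.5 × (0.10)²] = 10.507 / 0.03 = 350.2, so 351; the plan states 360. No sample-size figure is in dispute here.

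**Size of the shift.** The documents give neither the frequency nor the OCR distribution, so the following are assumptions: OCR 1 to 6 at 50/30/8/2/9/1% in both arms; 0 antibiotic days on short course and 5 on standard course; affected short-course children with 3 days.

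*Bound.* Rescoring one child can lower that child's chance of a better result by at most 1. Hence 1% of an arm moves either index by at most 0.01, and one child in 180 by at most 1/180 = 0.0056.

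*OCR index.* A child's score is the share of the other arm that is worse plus half the share that is equal.

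- OCR 1: 0.50 + 0.25 = 0.75. OCR 2: 0.20 + 0.15 = 0.35. OCR 3: 0.12 + 0.04 = 0.16. OCR 4: 0.10 + 0.01 = 0.11. OCR 6: 0.005.
- Average over the OCR 1 to 4 mix: (0.5 × 0.75 + 0.3 × 0.35 + 0.08 × 0.16 + 0.02 × 0.11) / 0.9 = 0.55.
- Moving 1% from that mix to OCR 6: 0.01 × (0.55 − 0.005) = 0.0055 (0.00545 unrounded).
- Moving 1% from OCR 1 to OCR 6: 0.01 × (0.75 − 0.005) = 0.0075 (0.00745 unrounded).

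*DOOR, from OCR 1, short-course arm only.* With 3 days against 5, an OCR 1 child beats every standard-course child (1.00); at OCR 6 the child beats only the 1% who are also at OCR 6 (0.01). The shift per 1% is 0.01 × 0.99 = 0.0099.

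| Short-course children affected | DOOR as written | DOOR rescored | OCR index as written | OCR index rescored |
|---|---|---|---|---|
| 1% | 0.681 | 0.671 | 0.503 | 0.495 |
| 2% | 0.684 | 0.664 | 0.505 | 0.490 |
| 5% | 0.694 | 0.644 | 0.513 | 0.475 |

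*Both arms affected at 1%.* The OCR shifts cancel. For DOOR, a standard-course child falls from 0.50 (beating only short-course children at OCR 2 or worse) to 0, which returns 0.0050. The net shift is 0.0099 − 0.0050 = 0.0049.

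**The case against.** The strongest reply is that the SAP does what the protocol's endpoint section asks. Table 1 is visit-based, and the antibiotic only qualifies which visits count. That stands. A reader might infer that the SAP departs from the protocol's primary endpoint, or that Table 1, SAP 6.5.1 and protocol 9.5.2 give three different answers. The documents do not support either reading. Table 1 and SAP 6.5.1 agree on a pneumonia antibiotic without a visit and on an antibiotic for an unrelated illness; only 9.5.2 differs.

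A reader might also infer that 9.5.2 makes an antibiotic for an unrelated infection a treatment failure. Its wording is unrestricted, but it sits under a bullet about inadequate responders, in the rules for stopping study product, and it does not mention unrelated infections. That inference should not be pressed.

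It can also be said that such children will be rare. Parents are told to contact their provider, staff refer symptomatic children for care, and the record review and history look for both visits and antibiotics. Table 57 has a row for other medically attended visits, so a telephone prescription might be entered as a visit. SAP 6.5.6 calls for queries that make concomitant medication records consistent with visit records. These points make the gap smaller but do not close it: neither document says that a telephone prescription is a visit, and the reconciliation serves the day count without feeding the response derivation.

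Finally, similar rescue in the standard arm would offset the bias. On the assumptions above that is fully true for the OCR index and about half true for DOOR.

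**Conclusion.** The point holds as a gap in the endpoint derivation that the SAP inherits from the protocol. A non-study antibiotic for pneumonia that is recorded only as a concomitant medication leaves the child an adequate response, in conflict with protocol 9.5.2 and 2.3.1 and with SAP 8.3.3, while the same record counts as antibiotic days.

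The number of children affected is unknown. On the assumed distribution, each 1% of one arm affected shifts the OCR index by about 0.005 to 0.007 and DOOR by up to about 0.010 in that arm's favor. The DOOR figure is at most one tenth of the 0.10 design effect, and the 0.01 ceiling per 1% does not depend on the distribution. It would be tempting to conclude that the gap could decide the primary result. Nothing in the documents supports that, since no rate of unrecorded visits or of rescue is given. The case for a change is that the derivation should not score a known rescue for the index pneumonia as a success, and that correcting it is cheap.

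**What to change.** 1. **Protocol.** Reconcile 9.5.2 with Table 1 so that one endpoint definition of inadequate response applies, limited to antibiotics for pneumonia or its complications. This concerns scoring only; when study product is stopped is a separate matter.
2. **SAP 6.5.1.** At each outcome visit, before the no-visit line, set response to inadequate when the concomitant medication form shows a non-study systemic antibiotic started in the window (Days 1 to 5, or Days 1 to 18) with pneumonia or a complication of it as the indication. SAP 6.5.5 then gives OCR 6 without hospitalization and needs no change.
3. **Table 1, row 6.** Widen the wording, in both documents, to cover this case.
4. **If the sponsor keeps the visit-based primary definition,** run the scoring in item 2 as a prespecified sensitivity analysis of DOOR and OCR at both visits.

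The cost is one derivation line per visit and wording changes to Table 1 and 9.5.2. Because row 6 belongs to the primary endpoint, widening it is a change to the endpoint definition and should be made as one. The alternative in item 4 costs one added analysis. No new data are needed: Listing 12 already carries the indication and start day for each concomitant medication.

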study systemic antibiotic for pneumonia), or for which MAVPLEUR, MAVCHTB, MAVVIDEO, MAVTHOR, or MAVSURG were YES (treatment for a complication of pneumonia, including drainage of pleural fluid, placement of a chest tube, video assisted thoracoscopic surgery, or thoracotomy procedures), then the subject did not have adequate clinical response at OAV#1. If the subject had a MAV from Day 1 to Day 5 for which MAVHOSP and MAVHPPN were both YES (subject was hospitalized for the treatment of pneumonia or pneumonia complications), then the subject did not have adequate clinical response at OAV#1. Otherwise, if the subject had a MAV from Day 1 to Day 5 and either MAVABRX was missing, MAVABRX was YES and MAVABCP was missing, or any of MAVPLEUR, MAVCHTB, MAVVIDEO, MAVTHOR, or MAVSURG were missing, then adequate clinical response at OAV#1 is missing. Otherwise, if a subject has one or more MAVs from Day 1 to Day 5, with no MAV indicating receipt of a non-study systemic antibiotic for pneumonia or treatment for a complication of pneumonia, including drainage of pleural fluid, placement of a chest tube, video assisted thoracoscopic surgery, or thoracotomy procedures and no hospitalization for treatment of pneumonia or pneumonia complications and no MAV missing data as described, then the subject has adequate clinical response at OAV#1. Note that for determining whether the medical treatment or hospitalization falls within the period of Day 1 to Day 5, the date of the initial MAV will be used (MAVVISDT), rather than specific dates of surgery or hospitalization entered on the MAV form.

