    (MAVABRX=YES and MAVABCP=missing) or
    MAVPLEUR= missing or
    MAVCHTB= missing or
    MAVVIDEO= missing or
    MAVTHOR= missing or
    MAVSURG= missing

then ACR_OAV1=missing
else ACR_OAV1=YES

```

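### The missing-data check for adequate clinical response leaves out the two hospitalization fields, so in a narrow set of cases an unknown hospitalization defaults to success in the OAV#1 pseudocode

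*SAP*

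**What the plan says.** SAP 6.5.1 derives ACR from medically-attended-visit (MAV) fields. Two pairs share the same structure, an event and its reason: MAVABRX with MAVABCP for an additional antibiotic, and MAVHOSP with MAVHPPN for a hospitalization. Five more fields record procedures.

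For a treated, surviving child who has OAV#1 and a MAV in Days 1 to 5, the rule has three steps.

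1. **ACR = NO** if an antibiotic was given for pneumonia, if any procedure field is YES, or if "MAVHOSP=YES and MAVHPPN=YES". Each condition is sufficient by itself.
2. **ACR = missing** if the antibiotic field is blank, or if an antibiotic was given with no reason entered ("MAVABRX was YES and MAVABCP was missing"). The same step then turns to the procedure fields, with the wording "or any of MAVPLEUR, MAVCHTB, MAVVIDEO, MAVTHOR, or MAVSURG were missing, then adequate clinical response at OAV#1 is missing".
3. **Everything else.** The pseudocode ends with "else ACR_OAV1=YES". The prose grants a response if no MAV shows pneumonia treatment, there was no hospitalization for pneumonia, and no MAV data are missing in the sense just described.

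The OAV#2 prose, for Days 1 to 18, repeats the pattern: "or any of MAVPLEUR, MAVCHTB, MAVVIDEO, MAVTHOR, or MAVSURG were missing, then adequate clinical response at OAV#2 is missing". The printed pseudocode covers OAV#1 only.

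**The concern.** MAVHOSP and MAVHPPN are the only listed ACR inputs that can produce a NO but are absent from the missing-data step. The SAP treats an antibiotic with an unrecorded reason as unknown. For a hospitalization with an unrecorded reason, the pseudocode gives a response.

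This matters because of what follows from ACR:

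- SAP 6.5.5 assigns OCR 7, the worst non-fatal rank, only after ACR = NO. A child with ACR = YES goes on to ranks 1 to 5, or to missing because of some other component.
- SAP 6.5.3 sets resolution of symptoms to absent when ACR is NO, so that component inherits the default as well.
- Because ACR is not flagged missing, it does not trigger multiple imputation (8.4.1) and does not exclude the child from the complete-case cohorts (6.3.2).
- The worst-case analysis (8.2.2.5 and 8.2.2.6), which is meant to assume the worst for unknown data in the short-course arm, leaves the child a responder.

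Protocol 2.3.1 names a lower rate of adequate clinical response as the potential risk of short-course therapy. A default to success is therefore the less cautious choice for this field.

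**Working it through.** The plan gives no figure to reproduce here; the check is of decision logic.

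**Inputs.** The SAP 6.5.1 pseudocode, applied to a child with study product recorded, alive, OAV#1 done and one MAV in Days 1 to 5.

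**Single cases, all fields not named set to NO:**

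| State | ACR as printed | ACR with the added condition |
|---|---|---|
| MAVHOSP YES, MAVHPPN YES | NO | NO |
| MAVHOSP YES, MAVHPPN NO | YES | YES |
| MAVHOSP YES, MAVHPPN missing | YES | missing |
| MAVHOSP missing | YES | missing |
| MAVABRX YES, MAVABCP missing | missing | missing |

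**How wide the gap is.** Fix MAVHOSP = YES with MAVHPPN missing, and vary the rest. The antibiotic pair has 5 states: not given; missing; given with reason YES, NO or missing. The five procedures have 3^5 = 243 states. The total is 5 × 243 = 1,215.

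- NO: antibiotic for pneumonia, 243 states. In the other 4 antibiotic states, at least one procedure is YES in 243 − 2^5 = 211 states, so 4 × 211 = 844. Together 243 + 844 = 1,087.
- YES: all five procedures NO, with either no antibiotic or an antibiotic recorded as not for pneumonia: 2.
- Missing: 1,215 − 1,087 − 2 = 126.

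With MAVHOSP itself missing the counts are the same: 1,087, 126 and 2. After the added condition, NO stays at 1,087, missing becomes 128 and YES becomes 0. Only the two affected states change. These are counts of field combinations, not probabilities.

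**Prose.** Its last step requires that there was no hospitalization for pneumonia. With the reason blank, that cannot be decided. Its other safeguard, no missing MAV data, points back to a list without the hospitalization fields. The prose for both visits therefore leaves these states undetermined, while the pseudocode resolves them to YES at OAV#1.

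**Size per child.** The DOOR probability is U/(n1·n2) (SAP 8.1.1). One short-course child takes part in n2 comparisons, so moving that child across the whole scale changes U by at most n2, and the probability by at most n2/(n1·n2) = 1/n1. The same argument gives 1/n2 for a standard-course child. With 200 per arm this is 1/200 = 0.005. The planned effect is 0.60 − 0.50 = 0.10, so the bound is 0.005/0.10 = 5% of it.

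**The case against.** A reader might infer that any hospitalized child with an unrecorded reason is scored as an adequate response. The documents do not support that. A child with an antibiotic or procedure recorded for pneumonia is already NO. One with no such positive entry but a missing antibiotic or procedure field is already missing. Nor do the documents show that a known OCR 7 is recorded as a better rank: with the reason blank, or MAVHOSP blank, the true rank is unknown.

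The strongest defence comes from footnote 1 to Table 1, which defines persistent or worsening pneumonia by receipt of a non-study antibiotic for pneumonia or treatment for a complication. If all those fields are recorded and negative, the definition is arguably answered whatever MAVHPPN says. This does not settle the matter. SAP 6.5.1 makes a hospitalization for pneumonia sufficient by itself for ACR = NO, so its reason can decide the result even when the other fields are negative.

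Three further points stand as limits:

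- The prose is ambiguous and does not plainly say YES, and for OAV#2 there is only prose.
- Missing data are queried with sites (Protocol 13), entry checks flag incomplete records (15.2), and staff review the health record before OAV#1 when possible (7.3). This makes a blank reason at database lock less likely, but it is not an analysis rule.
- A recorded hospitalization still counts in the any-reason analysis if the child is in the complete-case cohort (SAP 8.2.5, Tables 27 and 29), and hospitalizations appear in Listings 13 and 14. The event is not hidden; only its place in the composite is affected.

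**Conclusion.** The omission is real and narrow. In the OAV#1 pseudocode, a child whose other MAV fields are all recorded, with none positive for pneumonia, is scored ACR = YES when MAVHOSP is missing, or when MAVHOSP is YES and MAVHPPN is missing. No other section supplies a rule for either blank. The prose at both visits shares the omission and leaves the case open.

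Each such child can move the DOOR probability by at most 0.005, assuming 200 per arm. The documents do not say how many there would be. The effect of the fix on the primary analysis is probably smaller than that bound. The fix makes DOOR missing, not a failure, and SAP 8.4.1 would impute it from site, treatment, strata, the other visit's OCR and daily symptom grades. Hospitalization is not among those predictors, so the imputed value would tend towards that of similar complete cases, not rank 7.

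It might be tempting to conclude that the primary result is in doubt. Nothing in the documents supports that. This is a minor correction worth making because it brings the hospitalization fields into line with the SAP's own antibiotic rule.

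**What to change.** In SAP 6.5.1, add this to the conditions that set ACR to missing: MAVHOSP=missing or (MAVHOSP=YES and MAVHPPN=missing). Put it in the prose for OAV#1, the prose for OAV#2 and the OAV#1 pseudocode, after the ACR = NO step, so that a child with another recorded pneumonia event stays NO. The imputation and the worst-case analysis will then treat such a child as unknown, and the complete-case cohorts will exclude the child for missing ACR.

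The cost is one line in each of three places and one line of program code. Nothing changes in data collection, sample size or the primary test. It is best done before unblinding.
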